5.4 Statistical models

5.4.1 Primary analysis

Analysis of time to events Data

Hypothesis and test statistic

The below description is for PFS

The null hypothesis stating that PFS survival distributions of the two treatment groups are equivalent will be tested against one-sided alternative.

Assuming proportional hazards for PFS, the following statistical hypotheses will be tested:

$$H_{01}: \theta_1 \geq 1 \text{ vs. } H_{A1}: \theta_1 < 1$$

where θ_1 is the PFS hazard ratio (Lutathera arm vs Octreotide arm).

Stratified log-rank test adjusting for the strata used in the randomization will be implemented as follows: In each of the K strata separately, the LIFETEST procedure with STRATA statement including only the treatment group variable and with the TIME statement will be used to obtain the rank statistic S_k and variance $\text{var}(S_k)$ where $k=1, 2, \dots, K$. The final test statistics will then be reconstructed as follows:

$$Z = [S_1 + \dots + S_K] / \sqrt{[\text{var}(S_1) + \dots + \text{var}(S_K)]}.$$

As a sensitivity analysis, unstratified Log-rank test will be used to test the difference between the treatment groups. The LIFETEST procedure in SAS with the TIME statement including a variable with survival times and a (right) censoring variable, and with STRATA statement including a variable for identifying treatment groups will be used. As an output of the procedure, the rank statistic S and variance $\text{var}(S)$ will be obtained. Under the null hypothesis, the test statistic $Z = S / \sqrt{[\text{var}(S)]}$ is approximately normally distributed.

Kaplan-Meier estimates

An estimate of the survival function in each treatment group will be constructed using Kaplan-Meier (product-limit) method as implemented in PROC LIFETEST with METHOD=KM option. The PROC LIFETEST statement will use the option CONFTYPE=LOGLOG.

Median survival for each treatment group will be obtained along with 95% confidence intervals calculated from PROC LIFETEST output using the method of [Brookmeyer and Crowley 1982](#). Kaplan-Meier estimates of the survival function with 95% confidence intervals at specific time points will be summarized. The standard error of the Kaplan-Meier estimate will be calculated using Greenwood's formula [\[Collett 1994\]](#).

Hazard ratio

Hazard ratio will be estimated by fitting the Cox proportional hazards model using SAS procedure PHREG (with TIES=EXACT option in the MODEL statement).

- For estimation without stratification the following applies. An unadjusted Cox model will be used, i.e., the MODEL statement will include the treatment group variable as the only covariate.
- For estimation with stratification the following applies. A stratified unadjusted Cox model will be, i.e., the MODEL statement will include the treatment group variable as the only covariate and the STRATA statement will include stratification variable(s).

Hazard ratio with two-sided 95% confidence interval will be based on Wald test.

Treatment of ties

The STRATA statement in LIFETEST procedure will be used to analyze time to event data with ties. The PHREG procedure in SAS with option TIES=EXACT will be used to fit the Cox proportional hazards model.

Checking proportionality of hazard assumption

Plots (SURVIVAL LOGSURV LOGLOGS) generated by LIFETEST procedure in SAS will be used to provide visual checks of the proportional hazard assumption.

- SURVIVAL plots estimated survivor functions. The shape of the curves should be basically the same if hazards are proportional.
- LOGSURV plots the cumulative hazard functions. The larger cumulative hazard should be a multiple of smaller if hazards are proportional
- LOGLOGS plots log (cumulative hazard). The LOGLOG plot will show parallel curves if hazards are proportional.

As an exploratory measure, to test the proportional hazard assumption, the treatment group * time interaction will be added in the MODEL statement in PHREG procedure in SAS. Evidence that interaction is not zero is evidence against proportional hazards. Further, the correlation between time and Schoenfeld residuals will be calculated to provide further evidence concerning the degree of proportionality.

Multiplicity adjustment

No adjustment for multiplicity will be applied. To protect the type I error for the primary and key secondary endpoints, these will be tested in a hierarchical fashion in the following order: PFS (centrally assessed), ORR, QoL Global Health (TTD), QoL Diarrhea (TTD), fatigue (TTD), and pain (TTD).

5.4.2 Key secondary analysis

Analysis of Binary Data (ORR)

The null hypothesis of equality of response rate in the two treatment arm will be tested against one-sided alternative. The statistical hypotheses are:

$H_0: ORRR \leq ORRC$ versus $H_A: ORRR > ORRC$, for a one-sided test

where ORRR is the probability of response in investigational arm and ORRC is the probability of response in control arm.

Both a stratified and an unstratified analysis will be presented.

The stratified analysis proceeds as outlined below.

The Cochran-Mantel-Haenszel chi-square test χ^2_{CMH} (implemented again via SAS procedure FREQ with CMH option in the TABLES statement) will be used to test the difference in response rates between the treatment arms. The p-value corresponding to the CMH test for “general association” will be used which follows a Chi-square distribution with one degree of freedom.

If the sampling assumptions for chi-square test is not met, the exact Cochran-Mantel-Haenszel test will be used (implemented via SAS procedure MULTTEST). The test is performed by running a stratified version of the Cochran-Armitage permutation test [Armitage et al. 1969]. In studies with stratified randomization, the chi-square approximation is considered appropriate for the χ^2_{CMH} statistics if the rule of Mantel and Fleiss [Mantel and Fleiss 1980] is satisfied.

The unstratified analysis proceeds outlined as below.

The Mantel-Haenszel chi-square test χ^2_{MH} (implemented via SAS procedure FREQ with CMH option in the TABLES statement) will be used to test the difference in response rates between the treatment arms. The p-value corresponding to the CMH test for “general association” will be used which follows a Chi-square distribution with one degree of freedom.

If the sampling assumptions for chi-square test is not met, Fisher’s exact test (implemented via SAS procedure FREQ with EXACT option in the TABLES statement) will be used to test the difference in response rates between the treatment arms. the rule for determining adequate sample size for χ^2 is that expected values should exceed 5 for all of the table cells.

Confidence interval for response rate

Responses will be summarized in terms of percentage rates with $100(1 - \alpha)\%$ confidence interval using exact binomial confidence interval (implemented using SAS procedure FREQ with EXACT statement for one-way table (Clopper and Pearson 1934).

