12.5.1 Key secondary objectives

If the primary endpoint is significant, the key secondary endpoints of overall response rate (ORR) and QoL will be tested in a hierarchical fashion to protect the type I error rate. The order of the hypothesis testing shall be ORR followed by QoL Global Health Scale (TTD, see below), followed by QoL Diarrhea (TTD), (TTD)-fatigue, and, (TTD)-pain (TTD). The key secondary objectives will be tested at the time of the primary analysis. At the final analysis, only a descriptive analysis will be performed.

Overall response rate (ORR) is defined as the proportion of subjects with best overall response (BOR) of complete response (CR) or partial response (PR), as per central review and according to RECIST 1.1.

ORR will be calculated based on the FAS and according to the ITT principle. ORR and its 95% confidence interval will be presented by treatment group. The Cochran-Mantel-Haenszel chi-square test, stratified by the randomization stratification factors, will be used to compare ORR

between the two treatment groups, at the 1-sided 2.5% level of significance. As a supportive analysis, ORR as per local review will be presented by treatment group, along with 95% confidence intervals.

Time to deterioration (TTD) is defined as time from randomization to the first deterioration of 10 points in domain score compared to the baseline score for the EORTC QLQ-C30 global health scale, diarrhea, fatigue, and pain assessments. The TTD distribution will be estimated using the Kaplan-Meier method, and the Kaplan-Meier curves, medians and 95% confidence intervals of the medians will be presented for each treatment group. Treatment effect will be tested by the stratified log-rank test. The hazard ratio for TTD will be calculated, along with its 95% confidence interval, using a stratified Cox model using stratified the randomization stratification factors. Patients with no baseline and/or no follow-up are censored at randomization. Diarrhea, fatigue and pain are considered clinically relevant (Strosberg, et al., 2018), identified as top symptoms in a patient survey (Singh, et al., 2018) and TTD associated with these symptoms domains was significant in a post-hoc analysis of NETTER-1.

Further details regarding the planned sensitivity and supplementary analyses for the key secondary endpoints will be provided in the SAP.

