2.6.1 Key secondary endpoints

If the primary endpoint is significant, the key secondary endpoints of overall response rate (ORR) and QoL will be tested in a hierarchical fashion to protect the type I error rate. The order of the hypothesis testing shall be ORR followed by QoL Global Health Scale (TTD, see below), followed by QoL Diarrhea (TTD), QoL fatigue (TTD), and, QoL pain (TTD).

Overall response rate (ORR) is defined as the rate of patients with best overall response of either unconfirmed partial response (PR) or unconfirmed complete response (CR), as per central review and according to RECIST 1.1. ORR will be calculated based on the FAS according to the ITT principle. Only tumor assessments performed before the start of any further anti-neoplastic therapies (i.e., any additional anti-neoplastic therapy or surgery) will be considered in the assessment of best overall response. Also patients with non-measurable lesions per central review at baseline will contribute to the ITT analysis, see [Table 2.6-1](#) below.

Table 2.6-1 Overall lesion response at each assessment: patients with non-target disease only

Non-target lesions	New lesions	Overall lesion response
CR	No	CR
Non-CR/Non-PD	No	Non-CR/Non-PD
UNK	No	UNK
PD	Yes or No	PD
Any	Yes	PD

EORTC QLQ-C30 includes 30 items. For more information regarding this instrument, see <https://www.eortc.org/app/uploads/sites/2/2018/02/SCmanual.pdf>. The following 9 scales and 6 single items are defined (where FS = Functional scale and SS = Symptom scale):

- Global health status / QoL (items 29 and 30)
- Physical functioning (FS) (items 1, 2, 3, 4 and 5)

- Role functioning (FS) (items 6 and 7)
- Emotional functioning (FS) (items 21, 22, 23 and 24)
- Cognitive functioning (FS) (items 20 and 25)
- Social functioning (FS) (items 26 and 27)
- Fatigue (SS) (items 10, 12 and 18)
- Nausea and vomiting (SS) (items 14 and 15)
- Pain (SS) (items 9 and 19)
- Dyspnoea (item 8)
- Insomnia (item 11)
- Appetite loss (item 13)
- Constipation (item 16)
- Diarrhoea (item 17)
- Financial difficulties (item 28)

For all scales the raw score (RS) is defined as the mean of the respective items:

$$RS = (item_{i_1} + item_{i_2} \dots + item_{i_n})/n$$

For a single item, RS is identical to the score of the item itself.

For the functional scales (FS), the score is calculated by the formula:

$$\text{Score} = \{1 - (RS - 1)/\text{range}\} \times 100.$$

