2.6.2 Statistical hypothesis, model, and method of analysis

ORR and its 95% confidence interval will be presented by treatment group.

The null hypothesis of the ORR in the investigational arm is less than or equal to the ORR in the control arm will be tested against the one-sided alternative. The statistical hypotheses are:

H_{02} : ORRR \leq ORRC versus H_{A2} : ORRR $>$ ORRC, for a one-sided test

where ORRR is the probability of response in investigational arm and ORRC is the probability of response in control arm.

The Cochran-Mantel-Haenszel chi-square test, stratified by the randomization stratification factors, will be used to compare ORR between the two treatment groups, at the 1-sided 2.5% level of significance. More details concerning the calculation are provided in [Section 5.4.2](#).

The analysis of QoL Time to Deterioration (TTD) will be the same as for PFS, employing log-rank test and Cox regression, see above, and, Appendix for further details.

Assuming proportional hazards model for TTD, the null hypothesis will be tested at one-sided 2.5% level of significance:

H_{01} (null hypotheses): $\Theta_1 \geq 0$ vs. H_{a1} (alternative hypotheses): $\Theta_1 < 0$,

where Θ_1 is the log hazard ratio of TTD in the Lutathera plus Standard Dose octreotide long-acting (30 mg) (investigational) arm vs. High Dose octreotide long-acting (60 mg) (control) arm.

For each domain, a Kaplan-Meier plot will be produced showing time to event by treatment arm. Kaplan-Meier methods will be used to generate a point estimate of the median time to event with corresponding 95% confidence interval (CI).

The stratified log-rank test will be used to compare the time to event in the two groups at the one-sided 2.5% level. The hazard ratios (HR) and corresponding 95% CIs were estimated from a stratified Cox proportional hazards model including randomized treatment as a factor. If too few events occur in any stratum (less than eight), then the main analysis will be unstratified. Both stratified and unstratified analyses will be presented.

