2.13 Interim analysis

There will be no interim analysis with inferential intent. But, at the time of the PFS primary analysis, an estimate of overall survival will be calculated in terms of hazard ratio (point estimate) and 95% confidence interval. Furthermore, a presentation of safety will be prepared including data from the time period up the interim.

3 Sample size calculation

The sample size calculation is based on the primary variable PFS. Assuming a median PFS in the control arm (High Dose octreotide long-acting (60 mg)) of approximately 15 months, it is hypothesized that treatment with Lutathera added to standard dose octreotide long-acting will result in a 50% reduction in the hazard rate (corresponding to an increase in median PFS from 15 months to 30 months).

To ensure 90% power to test the null hypothesis: PFS hazard ratio = 1, versus the specific alternative hypothesis: PFS hazard ratio = 0.50, it is calculated that a total of 99 PFS events need to be observed. This calculation assumes analysis by a one-sided log-rank test at the overall 2.5% level of significance, patients randomized to the two treatment groups in a 2:1 ratio. Assuming that enrolment will continue for approximately 22.2 months at a rate of 10 patients per month and a 15% dropout rate by the time of the final PFS analysis, a total of 222 patients (148 for Lutathera arm and 74 for the control arm) will need to be randomized to observe the targeted 99 PFS events at about 12.8 months after the randomization date of the last patient, i.e., 35 months after the randomization date of the first patient. If the final analysis is performed when the targeted 99 PFS events are observed, the observed hazard ratio will have to be < 0.658 which corresponds to a difference in median PFS of 7.8 months to declare statistical significance.

These calculations were made using the software package East 6.4.

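### SAP 5.4.2 names a two-sided, unsigned p-value for the one-sided 2.5% ORR test and does not say how to convert it

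*SAP*

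**What the plan says.** **Level and direction.** SAP 2.6.2 says that the stratified CMH test "will be used to compare ORR between the two treatment groups, at the 1-sided 2.5% level of significance". Protocol 12.5.1 sets the same level, "between the two treatment groups, at the 1-sided 2.5% level of significance". SAP 2.6.2 and 5.4.2 both write the null as an investigational response rate no higher than control and the alternative as higher. SAP 5.4.2 opens: "The null hypothesis of equality of response rate in the two treatment arm will be tested against one-sided alternative".

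**The p-value.** For the calculation, SAP 2.6.2 refers to SAP 5.4.2. There the general-association p-value from the SAS CMH output "will be used which follows a Chi-square distribution with one degree of freedom". The same sentence serves the stratified and the unstratified analysis. The fallbacks are an exact CMH test in PROC MULTTEST and Fisher's exact test in PROC FREQ. No tail is given for either.

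**Position in the hierarchy.** ORR follows PFS and precedes all the quality-of-life tests: "The order of the hypothesis testing shall be ORR followed by QoL Global Health Scale", then diarrhea, fatigue and pain.

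**The concern.** A chi-square statistic on one degree of freedom is the square of a Z statistic. Its p-value counts departures in both directions and does not show which arm did better. The plan pairs this p-value with a one-sided level and leaves out the step between them.

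The same appendix handles PFS differently. In SAP 5.4.1 the stratum rank statistics are summed and divided by the root of their summed variances ("The final test statistics will then be reconstructed as follows"), which gives a signed Z. Direction is therefore built into the PFS statistic but not into the p-value named for ORR.

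At stake is the rejection rule of a confirmatory test that gates four others. If the two-sided p falls where the readings differ, success on ORR and the opening of the TTD tests would depend on a programming choice that neither document fixes.

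**Working it through.** **Inputs.** One-sided 2.5% and a directional alternative (protocol 12.5.1, SAP 2.6.2); general-association p on 1 df (SAP 5.4.2); "a total of 222 patients (148 for Lutathera arm and 74 for the control arm) will need to be randomized" (SAP Section 3). The documents give no response rates, and SAP 3.1 states that power was not calculated for the key secondary variables. All ORR rates below are therefore assumptions.

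**1. The plan's own one-sided figures.** For PFS with hazard ratio 0.50, 90% power and 2:1 allocation:
- Events = (1.960 + 1.282)² / [(2/9) × (ln 0.5)²] = 98.4, rounded up to 99, as stated.
- Critical hazard ratio = exp(−1.960 / √(99 × 2/9)) = 0.6585, matching the stated 0.658.

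The design figures for PFS therefore use Z > 1.960 as one-sided 2.5%.

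**2. The ORR level under each reading.** With chi-square = Z², the named p-value is p = 2 × P(Z > |z|).

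| Rule | Chi-square cut-off | Z cut-off | Level, favouring Lutathera | Level, favouring control |
|---|---|---|---|---|
| Named p < 0.025, taken directly | 5.024 | \|Z\| > 2.241 | 1.25% | 1.25% |
| p/2 < 0.025 and difference favours Lutathera | 3.841 | Z > 1.960 | 2.50% | 0 |

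Only the second rule gives the stated level, and it is not written down.

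**3. Simulated level.** Stratified CMH, 148 versus 74 patients, four strata with assumed shares of 35/30/20/15%, common response rates of 5% to 30%, 400,000 draws each. The direct rule rejects in favour of Lutathera in 0.6% to 1.2% of trials and in favour of control in 1.3% to 1.5%. The signed rule rejects in favour of Lutathera in 1.7% to 2.4%. Both lie below nominal in the favourable direction because the data are discrete.

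**4. Power.** Exact binomial enumeration of the unstratified pooled Z test, 148 versus 74:

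| Assumed ORR, Lutathera vs control | Z > 1.960 | Z > 2.241 | Loss (points) |
|---|---|---|---|
| 15% vs 5% | 62% | 49% | 13 |
| 25% vs 10% | 79% | 69% | 10 |
| 40% vs 20% | 87% | 80% | 7 |
| 30% vs 10% | 95% | 90% | 4 |
| 40% vs 10% | 99.9% | 99.8% | 0.1 |

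Simulating the stratified CMH test (100,000 draws per scenario) gives nearly the same results: 62% to 49%, 79% to 69%, 95% to 90% and 99.9% to 99.8% for the first, second, fourth and fifth rows.

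**5. When the readings disagree.** With the effect favouring Lutathera, they differ only for chi-square between 3.841 and 5.024, that is, two-sided p between 0.025 and 0.05. With the effect reversed, they differ whenever the two-sided p is below 0.025.

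**The case against.** The strongest reply is that SAP 5.4.2 never sets its p-value against 0.025. The level is called one-sided in both documents, and the hypotheses are directional wherever they appear. The only reading that respects all of this is half the two-sided p, in the favourable direction, against 0.025. An experienced programmer would probably do that without being told.

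Much of this stands, and it rules out three stronger readings that a reader might draw:

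- *That the ORR test runs at 1.25%.* The documents do not say so. The 1.25% follows only if the named p-value is compared directly with the named level.
- *That the plan would accept a result favouring control.* The written null already includes a lower response rate with Lutathera, so such a result cannot support the claim. Response rates with confidence intervals are presented by arm, so the direction would be visible.
- *That type I error is inflated.* The direct reading is stricter than intended for a Lutathera claim.

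The reply does not supply the missing step. SAP 5.4.2 is specific about which p-value is used, and that p-value does not fit the stated level as it stands. The section's directional hypotheses suggest a one-sided tail for the exact tests, but the text does not specify one.

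**Conclusion.** The point holds as a mismatch between a stated level and a named p-value, with no conversion rule. Read directly, the level in favour of Lutathera is 1.25% where 2.5% is stated. That figure is asymptotic and conditional on the direct comparison.

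The error is on the conservative side. Its cost is power for ORR, and through the hierarchy for the four TTD tests: about 0 to 13 points over the assumed rates tried. The loss is largest for modest differences such as 15% versus 5% and negligible for a large one such as 40% versus 10%. The documents contain no ORR assumption that would place the trial within this range.

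The correction should be made because ORR is a gatekeeper and its rejection rule ought to be fixed before the data are seen. It does not call the design or the PFS test into question.

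**What to change.** Add to SAP 5.4.2, for the stratified and the unstratified analysis: the one-sided p-value is 1 − Φ(Z), where Z is the square root of the CMH statistic, signed positive when the response rate is higher with Lutathera, and it is compared with 0.025. State also that the MULTTEST exact CMH test and Fisher's exact test use the upper-tail one-sided p-value, in the direction of a higher response rate with Lutathera.

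The cost is a sentence or two in the SAP before database lock. Sample size, the hierarchy and data collection are unchanged, and ORR then keeps direction in the same way as PFS.

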5.4.3 Special statistical methods for OS analysis

Patients who progressed on Octreotide LAR are allowed to cross-over to open-label Lutathera. However, Octreotide LAR patients who switch to Lutathera after they progress are likely to benefit from the delayed administration of Lutathera and, therefore, the survival treatment estimate becomes confounded. Under such circumstances, the statistical test of the treatment effect is known to be biased towards the null hypothesis of no difference (Robins and Tsiatis 1991; Korhonen et al 1999; Greenland et al 2008).

However, with the inclusion of Lutathera re-treatment for some patients randomized in the Lutathera investigational arm, these patients may have increased OS compared to those who do not receive Lutathera re-treatment after central progression.

Therefore, the following modeling approaches will be used to obtain an estimate of survival treatment effect corrected for treatment cross-over and re-treatment: ‘Rank-preserving

structural failure time method' and 'Cox model with Inverse Probability of Censoring Weighting'. More details are provided in sections below. Should a patient have switched prior to progression (locally or centrally confirmed), that patient will be analysed similarly to those that switched after progression.

Despite the cross-over and re-treatment design, a supportive analysis of OS will use the strict intention-to-treat (ITT) approach, i.e., 'analyze as randomized' and ignore the treatment switch or re-treatment with Lutathera (and ignore additional anticancer therapies administered after study treatment discontinuation).

